10.2.4 Rationale for primary endpoint

The main clinical objective of BASILICA is to allow TAVR without causing death from acute coronary artery obstruction in patients identified at baseline because of existing valve design and geometry. The primary endpoint is selected to provide a binary summary assessment of procedure success to help assess the clinical utility of the investigational procedure.

10.2.5 Independent Clinical Events Adjudication

An independent Clinical Events Adjudication Committee will review all of the following that occur in the first year:

- Deaths
- Primary endpoints
- Site-reported strokes

The CEAC will classify relatedness of the above events to the BASILICA procedure. The PI and the CEAC will agree on a charter, but only after the CEAC contract is awarded. CEAC adjudication prevails over PI classifications.

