6.0 STUDY DESIGN

6.1 Schematic of Study Design

6.2 Overview of Study Design

This is a prospective, open-label, single-arm, multi-center, investigator-initiated, independently-adjudicated trial of BASILICA immediately before TAVR in subjects at high risk of coronary artery obstruction.

Candidates will be identified by the participating structural heart disease programs. In evaluation of aortic valve disease, candidates will undergo clinical evaluation, echocardiography, and contrast-enhanced gated cardiac CT. Eligibility will be reviewed and proposed by the local multidisciplinary heart teams. Candidates will then undergo central eligibility review by the sponsor and designated investigators. If deemed eligible, candidates will be offered participation in the study.

Once enrolled, subjects will undergo baseline assessment and blood tests.

Subjects will be admitted to the hospital and undergo TAVR with BASILICA. They will undergo endpoint assessment before discharge, after 30 days, and then 12 months.

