6.4 BASILICA TAVR Procedure

The BASILICA TAVR procedure is planned from a contrast-enhanced CT of the heart to select a suitable transcatheter heart valve size, predict suitability of the sub- and supra-annular landing zone, and predict post-TAVR coronary obstruction related leaflet encroachment on the sinotubular junction and coronary artery ostia. Knowledge of the aortic valve operative history is integrated into this assessment. These data are used to select a BASILICA traversal point, radiographic landmarks, and fluoroscopic projection angles.

The procedure is performed under general anesthesia or under moderate sedation at the discretion of the institutional heart team. The BASILICA procedure has three steps: (1) leaflet traversal with a guidewire, followed by (2) leaflet laceration, immediately followed by (3) TAVR. These are all guided by fluoroscopy and adjunctive echocardiography as needed.

Research study participation is defined as beginning the moment BASILICA traversal is attempted.

First catheter access is obtained typically via four arterial introducer sheaths (two for BASILICA, one for hemodynamics and angiography, and one for TAVR) and at least one venous introducer sheaths for temporary transvenous pacing. Anticoagulation with heparin or equivalent achieves an activated clotting time > 300s.

Hemodynamic and echocardiography measurements are recorded at baseline including gradients across the aortic valve, severity of valvular obstruction and severity of valvular regurgitation.

Two retrograde catheters are positioned, using a guidewire anchor as needed, in the LVOT and Aorta respectively. Care is taken to avoid entrapment of mitral valvular structures. A snare catheter is positioned in the LVOT. A coaxial traversal guiding catheter system (typically tandem catheters) directs electrosurgery devices (typically a rigid 0.014" guidewire inside a polymer jacket wire convertor) against the base of the coronary cusp targeted for laceration, using fluoroscopic and/or echocardiographic guidance.

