10.2.3 Secondary Endpoints

Secondary endpoints include

- Technical success, defined as clinical success irrespective of coronary artery stenting
- Clinical success without stroke, as determined by site physicians
- Technical success of BASILICA only (delivery and removal of BASILICA catheter equipment, traversal, and laceration of intended aortic leaflet)
- Coronary artery obstruction measured as instantaneous wave-free pressure ratio (iFR) or related measurements using a solid-state pressure-transducer guidewire, if measured
- Survival to discharge, to 30d, and to 12mo
- Neurological events as reported by the site clinicians
- Access and vascular complications
- Peri-procedural and spontaneous acute myocardial infarction
- Pericardial effusion or tamponade
- VARC-2 bleeding complications
- AKIN acute kidney injury
- Freedom from hemolytic anemia related to BASILICA TAVR
- BASILICA Device or Procedure related technical failure: acute embolism, mitral valve injury, traversal into left atrium, coronary artery injury induced by BASILICA, etc.
- Rotational orientation of transcatheter heart valve commissures with regard to coronary artery ostia

- Hemodynamic instability caused by BASILICA before TAVR
- TAVR thrombosis on CT or echocardiography during follow-up
- Endocarditis during follow-up
- Outcomes for laceration of native versus surgical aortic valves, for single versus double scallop laceration, and for procedures with versus without bioprostheses intentional overexpansion

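### Stroke adjudication is triggered by the open-label site's own label, which skews ascertainment toward under-counting, and the stroke composite is left to site physicians with no stated window

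*Combined protocol and SAP*

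**What the plan says.** Section 6.2 describes a "prospective, open-label, single-arm, multi-center, investigator-initiated, independently-adjudicated trial of BASILICA". Section 10.2.5 sets the committee's scope: "An independent Clinical Events Adjudication Committee will review all of the following that occur in the first year", followed by three classes: deaths, "Primary endpoints" and "Site-reported strokes". Only the third class is qualified by who reported it. The committee's one explicit task is this: "The CEAC will classify relatedness of the above events to the BASILICA procedure". The section adds that committee decisions override PI classifications, and that a charter will be agreed once the committee's contract has been awarded.

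Two secondary endpoints in 10.2.3 concern the brain: "Clinical success without stroke, as determined by site physicians" and "Neurological events as reported by the site clinicians". Clinical success itself is defined in 10.2.1 and assessed when the subject leaves the catheterization laboratory. Neither secondary endpoint states a period over which stroke counts.

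Under 10.2, the site PI classifies events first and the NIH PI confirms.

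**The concern.** The plan collects a wider class of neurological events than stroke, and section 11.1 lists TIA and seizure beside stroke as anticipated effects. Yet no rule sends the wider class to the committee. The boundary between stroke and not-stroke is where independent review is most useful, and here it is drawn by investigators who know that every subject had BASILICA. A site that over-calls a stroke will have the case reviewed. A site that under-calls one may not. The expected error therefore leans one way.

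Section 12.2 names embolization causing stroke as an anticipated risk of BASILICA, while Appendix A rates electrosurgical thromboembolism, including stroke, at the lowest likelihood level. This trial supplies the prospective evidence on that rating, so a stroke count that leans low would appear to confirm it.

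The composite has a separate problem. One section assigns it to site physicians and another gives the committee the last word. The plan does not say which classification feeds the endpoint, or up to what time.

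**Working it through.** The plan gives no stroke rate, stroke threshold or stroke-based sample size, so there is no figure of its own to reproduce. The check is mainly a reading of the text, with arithmetic for scale.

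**Routes by which a stroke could reach the committee**

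| Event | Route in 10.2.5 | Assured? |
|---|---|---|
| Stroke the site calls stroke | Site-reported strokes | Yes |
| Fatal stroke the site attributes to another cause | Deaths | Yes, as a death |
| Non-fatal stroke within 30 days, labelled otherwise | Possibly through the 30-day MACE endpoint (10.2.2) | Not stated |
| Non-fatal stroke after 30 days, labelled otherwise | None described | No |

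The third row is uncertain for two reasons. The MACE components are not listed, only the VARC-2 reference. The plan also does not say whether the committee reviews all 30 subjects for the primary endpoints or only failures that the site has flagged. The other primary endpoint, clinical success in 10.2.1, has no stroke component.

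The schedules in 6.5 and 6.6 name no neurological examination, stroke scale or brain imaging that would bring out an unreported stroke independently of the site's label.

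**Time point of the composite.** Clinical success is fixed at laboratory exit (10.2.1). The stroke part has no stated window (10.2.3). If it took over the laboratory-exit time point, it would be judged very early, given that "The procedure is performed under general anesthesia or under moderate sedation at the discretion of the institutional heart team". If it ran to a later point, that point is missing. Both readings are open.

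**Size of one event.** N = 30 subjects with attempted BASILICA TAVR (10.1). One event is 1/30 = 3.3 percentage points. Exact (Clopper-Pearson) 95% intervals for x/30:

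| x | x/30 | 95% CI |
|---|---|---|
| 0 | 0% | 0 to 11.6% |
| 1 | 3.3% | 0.1 to 17.2% |
| 2 | 6.7% | 0.8 to 22.1% |
| 3 | 10.0% | 2.1 to 26.5% |

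**Chance of at least one stroke that the site does not report as stroke.** Let p be the true stroke risk and s the probability that the site labels a stroke as stroke. Both are assumptions, since the documents give neither. The chance is 1 − (1 − p(1 − s))^30.

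| p | s = 100% | s = 80% | s = 60% |
|---|---|---|---|
| 5% | 0 | 1 − 0.99^30 = 26% | 1 − 0.98^30 = 46% |
| 10% | 0 | 1 − 0.98^30 = 46% | 1 − 0.96^30 = 71% |
| 15% | 0 | 1 − 0.97^30 = 60% | 1 − 0.94^30 = 84% |

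This table ignores recovery through death or MACE review, so it gives the chance of a site miss and not of a final miss.

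**The case against.** A reader might infer that the committee sees only what the site already calls stroke, so that adjudication can remove strokes but never add them. The documents do not support that. Deaths and primary endpoints are reviewed without the site-reported qualifier, so a fatal stroke under another label reaches the committee, and MACE review could bring out others. Removal is itself an inference: the stated task is relatedness, and the precedence rule has no direction. For a composite determined wholly by site physicians, adjudication would change the count in neither direction.

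A reader might also infer that the composite is fixed at laboratory exit and so nearly equals plain clinical success. That is one reading of an unstated window.

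There are other checks on the site's label. The NIH PI confirms classifications and major adverse events are narrated case by case (10.2). New adverse events are reported through the 30-day visit and serious ones afterwards (11.2.3). A contract research organization compares case report forms with source documents (15.3). An event labelled TIA would still appear among neurological events. These points stand, but none amounts to independent adjudication of the diagnosis.

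Finally, the consequences are limited. The analysis is descriptive, the sample size is not statistically derived, the stopping rules use mortality only, and there is no second arm for differential labelling to bias. The two illustrative intervals overlap almost entirely. All of this stands and keeps the point modest.

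**Conclusion.** The concern holds in a limited form. The stroke-specific trigger for independent review is the open-label site's own report. Non-fatal events labelled otherwise have no assured route to the committee, and after 30 days no route is described. Ascertainment is therefore skewed toward under-counting, with some recovery possible through death and MACE review. Separately, 10.2.3 and 10.2.5 do not settle whose classification feeds the stroke composite, and its stroke window is missing.

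The size is 3.3 points per event. With assumed counts, one relabelled event moves 2/30 (6.7%) to 3/30 (10.0%). The true stroke risk and the accuracy of site labelling are unknown, and if sites label every stroke correctly the under-count is zero. No planned decision depends on the stroke count. This is a cheap improvement worth making and does not threaten the trial's main conclusions.

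**What to change.** 1. In 10.2.5, replace the site-reported-stroke item with all recorded neurological events, across the committee's existing one-year remit.
2. In the same section, state that the committee adjudicates the diagnosis (stroke or not) as well as relatedness. The charter, which is still to be agreed, can carry the working detail.
3. In 10.2.3, define the composite as clinical success at laboratory exit plus freedom from committee-adjudicated stroke through 30 days. Keep the site-determined version as a sensitivity row, so that any difference between the two is visible.

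The cost is a few extra dossiers for the planned committee and possibly a less favourable stroke figure. No new staff or examinations are needed. Section 6.7 lists the adjudication contract as a milestone, so the wider scope should be written in before it is awarded. One limit remains: after the 30-day visit only serious or unanticipated events go to the sponsor (11.2.3), so in later months the wider trigger would mainly bring in serious neurological events.

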10.3 Stopping Rules and Data Safety Monitoring

A Data and Safety Monitoring Board (DSMB) appointed by the NHLBI Division of Intramural Research will monitor the safety of subjects in the study as described in the investigational plan. All members of the DSMB are unaffiliated to the study. The NHLBI DSMB will review the protocol progress report at six month intervals, or more frequently upon request of PI, IRB, and/or NHLBI Clinical Director. The DSMB may recommend early termination of the study for considerations of safety and efficacy. Unanticipated Adverse Device Effects (UADEs) will be submitted to the DSMB following the same timelines as the IRB (See section 9.2.4).

In the case of death or serious UADE, if the sponsor and the principal investigator determine that the event presents an unreasonable risk to the participating subjects, the clinical trial will be terminated within 5 working days after making that determination and not later than 15 working days after the sponsor first receives notice of the effect. [21 CFR 812.46]. All clinical sites will be notified of this action.

Each institutional IRB will review all Serious Adverse Events, Unanticipated Adverse Device Effects, and Unanticipated Problems, and may choose to suspend or terminate the protocol based on those findings. We believe this will protect subject safety.

We propose different stopping rules based on whether the operator elects intentionally to over-expand the bioprostheses.

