10.3.2 Stopping Rules for no intentional overexpansion of bioprosthetic stratum

The study will be monitored to ensure that the mortality within 30-days after the procedure does not substantially exceed an anticipated rate. We anticipate the rate of 30-day mortality is 15% or less and determine the stopping rule by a Bayesian approach [8]. The stopping boundary is reached if the posterior probability that the 30-day mortality rate exceeds 15% is at least 90%. We take our prior distribution to be a beta distribution so that our prior clinical opinion is worth 20% of the weight we will place on the new study data, which gives the prior parameters $a = 0.9$, $b = 5.1$. Hence when we make decisions about stopping the study, the data from the study will dominate over the prior opinion.

The following table summarizes the threshold numbers for the stop rule boundary, which would lead to a recommendation to stop the study due to the excess 30-day mortality.

Number of subjects in the stratum	Stop if the number of deaths within 30 days reaches
2	2
3-6	3
7-11	4
12-16	5
17-21	6
22-26	7
27-30	8

We investigated the performance of the above stopping rule by a simulation study. In each simulation run, we generated a study with 30 independent Bernoulli trials, each with a true certain 30-day mortality, and compared these outcomes with the above stopping boundary to determine whether the study was stopped. We repeated the simulation 100,000 times and computed the proportion of stopped studies using the above stopping rule. The following table summarizes the performance of this stopping rule:

True 30-day mortality rate	10%	15%	20%	25%	30%	35%
Proportion of Stopped Studies	4.8%	17.3%	39%	62.3%	81.3%	92.2%
Average number of subjects	29.1	27	23.5	19.4	15.4	12.1
Average number of 30-day mortality	2.9	4	4.7	4.9	4.6	4.2

These simulation results suggest that our stopping rule has a low probability stopping a study when the true 30-day mortality rate is 15% or less, and the probability of stopping a study is high when the true 30-

day mortality rate exceeds 15%. There, we believe that our Bayesian stopping rule for 30-day mortality has satisfactory statistical properties.

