10.3.3 Stopping Rules for intentional overexpansion of bioprosthetic stratum

The study will be monitored to ensure that the mortality within 30-days after the procedure does not substantially exceed an anticipated rate. We anticipate the rate of 30-day mortality is 20% or less and determine the stopping rule by a Bayesian approach [8]. The stopping boundary is reached if the posterior probability that the 30-day mortality rate exceeds 20% is at least 90%. We take our prior distribution to be a beta distribution so that our prior clinical opinion is worth 20% of the weight we will place on the new data. This gives the prior parameters $a = 1.2$, $b = 4.8$. Hence when we make decisions about stopping the study, the data from the study will dominate over the prior opinion.

The following table summarizes the threshold numbers for the stop rule boundary, which would lead to a recommendation to stop the study due to the excess 30-day mortality.

Number of subjects in the "overexpansion of bioprosthetic stratum"	Stop if the number of deaths within 30 days reaches
3-5	3
6-8	4
9-12	5
13-16	6
17-20	7
21-24	8
25-28	9
29-30	10

We investigated the performance of the above stopping rule by a simulation study. In each simulation run, we generated a study with 30 independent Bernoulli trials, each with a true certain 30-day mortality, and compared these outcomes with the above stopping boundary to determine whether the study was stopped. We repeated the simulation 100,000 times and computed the proportion of stopped studies using the above stopping rule. The following table summarizes the performance of this stopping rule:

True 30-day mortality rate	10%	15%	20%	25%	30%	35%	40%
Proportion of Stopped Studies (%)	1.6%	6.9%	18.9%	38.3%	60.5%	78.5%	90.5%
Average number of subjects	29.6	28.7	26.7	23.6	19.7	16	12.7
Average number of 30-day mortality	3	4.3	5.3	5.9	5.9	5.6	5.1

These simulation results suggest that our stopping rule has a low probability stopping a study when the true 30-day mortality rate is 20% or less, and the probability of stopping a study is high when the true 30-day mortality rate exceeds 20%. There, we believe that our Bayesian stopping rule for 30-day mortality has satisfactory statistical properties.

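### Does the 30-day mortality stopping rule fail because no one is named to apply it between six-monthly DSMB reviews?

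*Combined protocol and SAP*

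**What the plan says.** Section 10.3 gives the DSMB general oversight: it "will monitor the safety of subjects in the study as described in the investigational plan". It is to "review the protocol progress report at six month intervals, or more frequently upon request of PI, IRB, and/or NHLBI Clinical Director", and it may recommend early termination. UADEs are the only events sent to it one by one.

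Sections 10.3.2 and 10.3.3 set the mortality rule for each stratum. "The study will be monitored to ensure that the mortality within 30-days after the procedure does not substantially exceed an anticipated rate" is written in the passive. The table is indexed by "Number of subjects in the stratum" and gives the number of 30-day deaths at which to stop, "which would lead to a recommendation to stop the study due to the excess 30-day mortality". Its performance was simulated as follows: "we generated a study with 30 independent Bernoulli trials".

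Four other provisions bear on how the rule works in practice:

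- **Enrolment.** It is marked by an attempted BASILICA (6.4, 6.6), and the target of 30 counts attempted procedures (10.1).
- **Death reports.** A death goes to the sponsor within 3 working days and to the NHLBI IRB within 7 days (11.2.4).
- **Adjudication.** Section 10.2.5 covers deaths: "An independent Clinical Events Adjudication Committee will review all of the following that occur in the first year".
- **Termination.** Section 10.3 also lets the sponsor and PI end the trial after a death that they judge to show unreasonable risk.

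**The concern.** A stopping rule protects subjects only if someone applies it in time. Here the comparison has no named owner. The DSMB's only fixed reviews are six months apart, in a trial meant to enrol within 12 months (6.7). Death is on the list of anticipated device effects (11.1), so an ordinary death need not reach the DSMB as a UADE. Read narrowly, the DSMB could learn of a crossing months after the sponsor held the reports.

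The denominator raises a second doubt. In the no-overexpansion stratum, 3 deaths among 6 subjects cross the boundary and 3 among 7 do not. Counting subjects who are still inside 30 days could therefore change a decision. If the rule in practice differed from the simulated one, the tables that are said to show satisfactory properties would not describe the trial.

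**Working it through.** **1. Reproduce the boundaries.** For each n, find the smallest k for which P(rate > p0) ≥ 0.90 under Beta(a + k, b + n − k).

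- No overexpansion (10.3.2): a = 0.9, b = 5.1, p0 = 0.15.
- Overexpansion (10.3.3): a = 1.2, b = 4.8, p0 = 0.20.

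Both printed tables are matched at every n up to 30. For example, 3 deaths in 6 gives Beta(3.9, 8.1) and a posterior probability of 0.921 (stop). 3 deaths in 7 gives Beta(3.9, 9.1) and 0.896 (continue).

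**2. Reproduce the performance.** Exact binomial recursion, with the boundary checked after every subject and the outcome already known:

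| Stratum, true mortality | Stopped, stated | Stopped, exact | Mean subjects, stated | Mean subjects, exact |
|---|---|---|---|---|
| No overexpansion, 15% | 17.3% | 17.5% | 27 | 26.9 |
| No overexpansion, 30% | 81.3% | 81.0% | 15.4 | 15.4 |
| Overexpansion, 20% | 18.9% | 19.2% | 26.7 | 26.7 |
| Overexpansion, 35% | 78.5% | 78.5% | 16 | 16.0 |

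The stated figures therefore assume a running check. Neither boundary falls as n rises, so another survivor can never cause a crossing. A check at each death is equivalent to a check after each subject.

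**3. Put the rule on the protocol's reporting clock.** The inputs below are assumptions except where a section is cited:

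- one stratum holding all 30 subjects;
- even or accelerating enrolment over 12 months (6.7);
- 4 days' notice of a death (near the 3 working days of 11.2.4);
- deaths spread over either 3 or 30 days;
- survivors known at day 30;
- a check at each reported death.

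| Quantity | Stated | Denominator: subjects treated | Denominator: known 30-day status |
|---|---|---|---|
| No overexpansion, stopped at 15% | 17.3% | 14.0-17.6% | 19.1-22.5% |
| No overexpansion, mean treated at 30% | 15.4 | 15.4-17.8 | 13.8-15.9 |
| Overexpansion, stopped at 20% | 18.9% | 14.3-19.3% | 20.9-25.5% |
| Overexpansion, mean treated at 35% | 16 | 16.0-18.7 | 14.5-16.4 |

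The table is indexed by subjects in the stratum, and a subject joins at attempted BASILICA, so the literal denominator is subjects treated. On that reading false stopping is at or slightly below the stated figure. The lower ends of the stopping ranges and the upper ends of the mean-treated ranges come from deaths spread over 30 days. In that case up to 17.8 − 15.4 = 2.4 more subjects are treated on average at 30% mortality, because later subjects enter before earlier deaths occur.

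**4. Bound the worst case.** Suppose the no-overexpansion boundary is read only at n = 15 and n = 30 (even enrolment, reviews at months 6 and 12, all outcomes known). At 30% mortality:

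- 75.0% of studies ever cross, against 81.0%;
- 48.5% stop before subject 30, against 79.5%;
- 22.7 subjects are treated, against 15.4, an excess of 7.3;
- 6.8 deaths occur, against 4.6, an excess of 2.2.

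False stopping at 15% falls from 17.5% to 10.1%. Other timings of the scheduled reviews give 20.2-24.0 treated and 6.1-7.2 deaths.

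**The case for a change.** The strongest reply is that an optional request is not a duty. This is an early trial in which lead investigators judged 30-day mortality of 15% or 20% acceptable (10.3.1), and this boundary is its only numerical stopping rule. No sentence obliges the PI or the IRB to call the DSMB when the table is reached. The sponsor/PI termination route rests on judgement and does not refer to the table. A few sentences would settle the matter.

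As a description of the text, that stands. No role is named, no crossing triggers a review, and subjects inside 30 days are not mentioned. Section 10.3 also points to a section 9.2.4 that does not exist. The reporting timeframes are in 11.2.4, so this is a clerical slip that misleads no one.

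The consequence does not stand. Rows starting at 2 or 3 subjects make sense only for a running count. The sponsor holds every death within days in an open-label trial of 30, and the NHLBI IRB, which is told of each death, may itself call the DSMB. The rule sits in the DSMB section and ends in a recommendation to stop, which is a power that section gives the DSMB. The investigational plan, which 10.3 cites for DSMB monitoring and which is not among the documents, may already assign the task.

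One apparent improvement would need care. Counting subjects in treatment order once their status is known keeps the stated proportions only if the boundary is also checked when survivors reach day 30. Checked at deaths alone, it stops about 78-80% at 30% mortality with about 17 treated, against 81.3% and 15.4 stated.

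**Conclusion.** No change to the plan is needed. The boundary is correctly derived, and its stated performance reproduces to within 0.3 percentage points. On its literal denominator, with a check at each reported death, it stops 14.0-17.6% of no-overexpansion studies at 15% mortality (stated 17.3%) and 14.3-19.3% of overexpansion studies at 20% (stated 18.9%). These ranges rest on one stratum of 30, 12-month enrolment and the assumed notice and timing of deaths. Smaller strata or slower reporting would move them.

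The excess of 7.3 subjects and 2.2 deaths in the worst case describes a trial in which the sponsor, PI and IRB all hold the death reports and leave the table unread until a scheduled review. The protocol does not direct that. What is missing is a record of who counts and who is told, a gap that a competent trial team fills without altering any threshold, table or analysis.

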10.0 BIOSTATISTICAL AND ANALYTICAL CONSIDERATIONS

10.1 Sample Size

The sample size is not statistically derived. This is a safety and feasibility study that enables patient access to a novel medical procedure, when these patients have no other good medical options to treat symptomatic aortic valve failure.

Up to 60 subjects will be consented until 30 subjects undergo attempted BASILICA TAVR in this protocol.

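### The numerical 30-day mortality boundaries count deaths only within each stratum, so early deaths split across the two strata can reach no boundary

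*Combined protocol and SAP*

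**What the plan says.** The trial total is fixed in section 10.1: "Up to 60 subjects will be consented until 30 subjects undergo attempted BASILICA TAVR in this protocol". Section 10.3 then divides the monitoring of mortality: "We propose different stopping rules based on whether the operator elects intentionally to over-expand the bioprostheses".

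- **Section 10.3.2 (no intentional over-expansion).** The rule stops when the posterior probability of 30-day mortality above 15% is at least 90%, with a Beta(0.9, 5.1) prior. The table is indexed by "Number of subjects in the stratum". Its first boundary is 2 deaths in 2 subjects, then 3 deaths at 3 to 6 subjects.
- **Section 10.3.3 (intentional over-expansion).** The form is the same, with a 20% limit and a Beta(1.2, 4.8) prior, again counted on that stratum's subjects. Its first boundary is 3 deaths at 3 to 5 subjects.

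The consequence is study-wide in both sections. Reaching a boundary is described as something "which would lead to a recommendation to stop the study due to the excess 30-day mortality". No section gives a numerical mortality boundary for all 30 treated subjects.

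Section 10.3 also provides discretionary safeguards at trial level: DSMB review every six months or sooner on request, IRB power to suspend or terminate, and termination if the sponsor and principal investigator judge that a death shows unreasonable risk.

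**The concern.** Leaflet traversal and laceration are performed in every subject. A hazard in that step would cause deaths in both strata, and would show soonest in the combined count. The rules never look at that count. With a few subjects in each stratum, neither table may have enough to act on, while the combined experience is already poor. The action triggered is study-wide, but the evidence for it is counted only in parts.

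The gap matters most among the first handful of subjects, where a numerical rule can still spare later ones.

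**Working it through.** **Inputs.** Priors, limits, the 90% threshold and both tables come from 10.3.2 and 10.3.3; the total of 30 comes from 10.1. The documents give no expected share of over-expanded subjects, so 40% to 50% is assumed, with 20% and 60% shown as a range. Outcomes are taken as independent and known before the next subject is treated.

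**1. Reproducing the plan's tables.** For d deaths in n subjects, the posterior is Beta(a + d, b + n − d), and the boundary is the smallest d with P(rate > limit) ≥ 0.90. Every printed row of both tables reproduces. With 30 subjects in one stratum, exact recursion gives stopping of 17.5% at 15% mortality in 10.3.2 (plan: 17.3%) and 19.2% at 20% mortality in 10.3.3 (plan: 18.9%).

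**2. Early paths that cross nothing.**

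- Without over-expansion, 1 of 1: P(> 15%) = 0.746. With over-expansion, 2 of 2: P(> 20%) = 0.886. Both are below 0.90 and precede each table's first row. Total: 3 deaths in 3. This is the only split of 3 subjects that does so, because 2 of 2 without over-expansion (0.914) and 3 of 3 with it (0.958) both stop.
- Without over-expansion, 2 of 3 (0.879, the first two not both deaths), plus 2 of 2 with it (0.886). Total: 4 deaths in 5.

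As a yardstick only, Beta(1.2, 4.8) applied to the total gives P(> 20%) = 0.958 for 3 of 3 and 0.976 for 4 of 5.

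**3. How often.** With 40% over-expanded, the 3-of-3 path has probability 3 × 0.6 × 0.4² × 0.3³ = 0.0078 at 30% mortality in both strata. With both strata at their limits it is 3 × 0.6 × 0.4² × 0.15 × 0.2² = 0.0017. The 4-of-5 path has probability about 0.4% at 30% mortality.

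**4. Effect of also checking the total against the printed 10.3.3 table.** Exact recursion over 30 subjects, each assigned at random to a stratum; each cell reads two tables → two tables plus total.

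| Share over-expanded | Stop within first 5, 30% mortality | Mean subjects treated, 30% mortality | Stop at any time, 30% mortality | Stop at any time, strata at 15% and 20% |
|---|---|---|---|---|
| 20% | 14.1% → 19.4% | 16.8 → 16.1 | 78.1% → 78.8% | 20.3% → 21.2% |
| 40% | 11.4% → 19.1% | 17.7 → 16.6 | 75.0% → 76.7% | 22.3% → 23.8% |
| 50% | 10.8% → 18.8% | 18.1 → 16.9 | 73.0% → 75.3% | 22.6% → 24.4% |
| 60% | 10.6% → 18.4% | 18.6 → 17.2 | 70.6% → 73.6% | 22.6% → 24.6% |

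The early gain comes mostly from 3 deaths among the first 4 or 5 subjects split between strata, not from the extreme paths in step 2. With both strata at their limits, stopping within the first 5 rises from 2.8% to 4.9% (40% over-expanded) or from 2.8% to 5.0% (50%).

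**The case against.** The separate rules are deliberate. Section 10.3.1 explains that valve fracture is assumed to add mortality and gives a different acceptable rate for each group. The 20% figure was elicited for fracture alone, so the plan has no criterion for the mixed population. A reader might infer that the plan breaches its own 90% criterion on the total. It does not, because that criterion is defined only within strata.

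A reader might also infer that a third of the trial could die unnoticed, since 10 deaths in 30 (for example 5 of 17 plus 5 of 13) can cross neither table. The arithmetic is right but the inference is weak. At 30% mortality, 10 or more deaths without a crossing occurs in about 0.05% of trials with 40% over-expanded and 0.14% with 50%. A boundary first reached at the thirtieth subject also spares nobody.

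Nor would three early deaths pass unseen. Section 11.2.4 requires deaths to reach the sponsor within 3 working days and the NHLBI IRB within 7 days. Section 10.2.5 sends every first-year death to independent adjudication. The bodies named in 10.3 can stop the trial.

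Finally, the added check discriminates little over the whole trial: at 40% to 50% over-expanded, stopping rises by about 2 points both at 30% mortality and at the limits.

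All of this stands, and it limits the point's weight. It does not close the gap. The safeguards are discretionary, and the plan chose numerical boundaries in addition to them. A total check leaves the stratum limits untouched. Its gain is in timing.

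**Conclusion.** The gap is real and modest. The two tables can be silent on early deaths that would stop the study if they fell in one stratum. The documents do not support saying that the trial has no protection against this, or that an existing rule on the total is violated.

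At 30% mortality in both strata and 40% to 50% over-expanded, a check on the total raises stopping within the first 5 subjects from about 11% to 19%. It lowers mean subjects treated by about 1.1 to 1.3 and raises overall stopping by about 2 points. The early gain is smaller if few subjects are over-expanded (14.1% to 19.4% at a 20% share). These figures assume that each 30-day outcome is known before the next subject is treated; enrolment that outruns follow-up would reduce the benefit of any of the three checks.

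**What to change.** Keep both stratum tables. Add one sentence to section 10.3: the stopping recommendation is also triggered when total 30-day deaths among all treated subjects reach the printed 10.3.3 (20%) table, read at the total number treated. Describe it as an added safety net at the looser of the two stated limits, not as an existing criterion of the plan.

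Add a line giving whole-study stopping probabilities for the three checks together, over a stated range of over-expansion shares. The current performance tables each simulate 30 subjects in one stratum, although 30 is the trial total, so no whole-study figure is available.

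The cost is one sentence and a rerun of the simulation. The statistical price, with both strata exactly at their limits and 40% to 50% over-expanded, is a rise in whole-study stopping of about 1.5 to 2 points, from about 22% to 24%.
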